8.1.6.2 Treatment Period

8.1.6.2.1 Dose Escalation

The first 3 enrolled patients will be treated with 100 mg of MK-3475 every 3 weeks for 6 cycles. If one subject of the three requires the dose of MK-3475 to be withheld or discontinued, the 100 mg cohort will be expanded to 6 subjects. If two out of three or two out of six subjects develop toxicity that requires the dose to be withheld or discontinued, the dose will not be escalated to 200 mg MK-3475 every 3 weeks. All remaining subjects will be treated at 100 mg MK-3475 every 3 weeks for 6 cycles.

Physical examination and assessment of toxicity will be performed before each administration of MK-3475. A CBC will be obtained on Day 1 of every 3-week cycle. Biochemistry panel examining electrolytes, and liver enzymes will be performed on Day 1, Cycle 1 of MK-3475, at Weeks 7, 10 and 13, and at the end of therapy (Week 19). Treatment will not proceed unless laboratory values are acceptable. Urinalysis will occur at weeks 7-12 prior to each BCG treatment. BCG treatment will not proceed unless urinalysis results are acceptable. Collect and record non-serious and serious adverse events and assignment of toxicity grade (NCI CTCAE, Version 4) at each visit. Collect and record any changes in concomitant medication.

Product: MK-3475

Protocol/Amendment No.: Amendment 5, 21 October 2019

Subjects will be provided with an oral thermometer and a diary (Appendix H) to document twice daily oral temperatures. The diary will also ask for documentation of other symptoms to help monitor for systemic infection of BCG.

The AUA IPSS and QOL questionnaires are to be administered at Day 1 Cycle 1 and Week 10 visit prior to any study procedures.

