5.2.3.3 Dose Modification (Escalation/Titration/Other)

Adverse events (both non-serious and serious) associated with pembrolizumab exposure may represent an immunologic etiology. These adverse events may occur shortly after the first dose or several months after the last dose of treatment. Pembrolizumab must be withheld for drug-related toxicities and severe or life-threatening AEs as per Table 3 below. See Section 5.4.1 for supportive care guidelines, including use of corticosteroids.

Table 3

Dose Modification Guidelines for Drug-Related Adverse Events

Toxicity	Hold Treatment For Grade	Timing for Restarting Treatment	Treatment Discontinuation
Diarrhea/Colitis	2-3	Toxicity resolves to Grade 0-1	Toxicity does not resolve within 12 weeks of last dose or inability to reduce corticosteroid to 10 mg or less of prednisone or equivalent per day within 12 weeks
	4	Permanently discontinue	Permanently discontinue
AST, ALT, or Increased Bilirubin	2	Toxicity resolves to Grade 0-1	Toxicity does not resolve within 12 weeks of last dose
	3-4	Permanently discontinue (see exception below) ^a	Permanently discontinue
Type 1 diabetes mellitus (if new onset) or Hyperglycemia	T1DM or 3-4	Hold pembrolizumab for new onset Type 1 diabetes mellitus or Grade 3-4 hyperglycemia associated with evidence of beta cell failure	Resume pembrolizumab when patients are clinically and metabolically stable
Hypophysitis	2-4	Toxicity resolves to Grade 0-1. Therapy with pembrolizumab can be continued while endocrine replacement therapy is instituted	Toxicity does not resolve within 12 weeks of last dose or inability to reduce corticosteroid to 10 mg or less of prednisone or equivalent per day within 12 weeks
Hyperthyroidism	3	Toxicity resolves to Grade 0-1	Toxicity does not resolve within 12 weeks of last dose or inability to reduce corticosteroid to 10 mg or less of prednisone or equivalent per day within 12 weeks
	4	Permanently discontinue	Permanently discontinue
Hypothyroidism		Therapy with pembrolizumab can be continued while thyroid replacement therapy is instituted	Therapy with pembrolizumab can be continued while thyroid replacement therapy is instituted
Infusion Reaction	2 ^b	Toxicity resolves to Grade 0-1	Permanently discontinue if toxicity develops despite adequate premedication
	3-4	Permanently discontinue	Permanently discontinue

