7.0 TRIAL FLOW CHART

7.1 Study Flow Chart

Trial Period	Screening Phase	Treatment Week/Cycle											End of Treatment		Post Treatment
Treatment Week/ Title	Screening Visit ^a	1	4	7*	8*	9*	10*	11*	12*	13	16	19	Discontinuation	Safety FU 20	Follow-Up Visit
Scheduling Window (Days)	-28 to -1	+/- 3	+/- 3	+/- 1	+/- 1	+/- 1	+/- 1	+/-1	+/-1	+/- 3	+/- 3	+/- 3	At time of Discontinuation	30 days Post discontinuation	3,6,9,12,18,24 Post cyst
Administrative Procedures															
Informed Consent	X														
Inclusion/ Exclusion Criteria	X														
Subject Identification card ^e		X													
Demographics and Medical History	X														
Prior and concomitant Medication Review ^f	X	X-----X													
Post-study anti-cancer therapy status ^g															X
Recurrence status ^g													X		X
Questionnaires ^h		X					X					X			X
Phone Call ^h				X	X	X	X	X	X						

Product: MK-3475

Protocol/Amendment No.: Amendment 5, 21 October 2019

Trial Period	Screening Phase	Treatment Week/Cycle											End of Treatment		Post Treatment
Treatment Week/ Title	Screening Visit ^a	1	4	7	8	9	10	11	12	13	16	19	Discontinuation ^c	Safety FU ^c 20	Follow-Up Visit ^d
Scheduling Window (Days)	-28 to -1	+/- 3	+/- 3	+/- 1	+/- 1	+/- 1	+/- 1	+/- 1	+/- 1	+/- 3	+/- 3	+/- 3	At time of Discontinuation	30 days Post discontinuation	3,6,9,12,18,24 Post cyst
Clinical Procedures/ Assessments															
Restaging Ta T1 tumors/ Possible Transurethral Resection ⁱ	X														
Review Adverse Events ^j	X	X-----X													
Physical Exam ^k	X ^k	X	X	X			X			X	X	X	X ^k	X ^k	
Performance Status ^l	X			X						X		X	X	X	
Vital Signs and Weight	X	X	X	X	X	X	X	X	X	X	X	X	X	X	
ECG ^m	X														
Chest X-Ray ⁿ	X ^q														
Pulmonary Function Tests ^m	X														
Laboratory Procedures/ Assessments: Analysis provided by Local Laboratory															
CBC w/ differential	X	X ^r	X	X			X			X	X	X	X	X	
CMP	X	X ^r		X			X			X		X	X	X	
Urinalysis	X			X	X	X	X	X	X			X	X	X	X
T3, FT4, and TSH	X			X									X	X	
Pregnancy Test (Urine or β-HCG)	X														
PT/INR and aPTT ⁿ As clinically indicated	X											X			
Hepatitis Panel	X														

Product: MK-3475

Protocol/Amendment No.: Amendment 5, 21 October 2019

Trial Period	Screening Phase	Treatment Week/Cycle											End of Treatment		Post Treatment
Treatment Week/ Title	Screening Visit ^a	1	4	7	8	9	10	11	12	13	16	19	Early Discontinuation ^b	Safety FU ^c 20	Follow-Up Visit ^d

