8.1.3.1 Laboratory Safety Evaluations (Hematology, Chemistry and Urinalysis)

Laboratory tests for hematology, chemistry, urinalysis, and others are specified in Table 7. The total amount of blood/tissue to be drawn/collected over the course of the trial (from pre-trial to post-trial visits), including approximate blood/tissue volumes drawn/collected by visit and by sample type per subject can be found in the Procedure Manual.

Laboratory tests for screening should be performed within 10 days prior to the first dose of treatment. If screening laboratory tests occur within this window, they do not have to be repeated on Day 1 of Cycle 1. After Cycle 1, pre-dose laboratory procedures can be conducted up to 72 hours prior to dosing. Results must be reviewed by the Investigator or qualified designee and found to be acceptable prior to each dose of trial treatment.

Remainder of Page Intentionally Left Blank

Product: MK-3475

Protocol/Amendment No.: Amendment 5, 21 October 2019

Table 7: Laboratory Tests

Hematology	Chemistry	Urinalysis	Other-only at specific time points
Hematocrit	Albumin	Blood	Serum β -human chorionic gonadotropin†
Hemoglobin	Alkaline phosphatase	Glucose	(β -hCG)†
Platelet count	Alanine aminotransferase (ALT)	Protein	PT (INR)
WBC (total and differential)	Aspartate aminotransferase (AST)	Specific gravity	aPTT
Red Blood Cell Count		Microscopic exam (If abnormal)	Total triiodothyronine (T3)
Absolute Neutrophil Count	Carbon Dioxide ‡ (CO₂ or bicarbonate)	results are noted	Free tyroxine (T4)
	Calcium	Urine pregnancy test †	Thyroid stimulating hormone (TSH)
	Chloride		Hepatitis Panel
			HA AbIgM, HBsAg HBcAb-IgM, HC Ab
	Glucose		TSH, free T4, prolactin, ACTH, and morning cortisol in case of suspected adrenal insufficiency
	Creatinine		Ketonuria testing in suspected hyperglycemia cases
	Potassium		
	Sodium		Urine for correlative studies
	Total Bilirubin		Blood for correlative studies
	Direct Bilirubin (If total bilirubin is elevated above the upper limit of normal)		
	Total protein		
	Blood Urea Nitrogen		
† Perform on women of childbearing potential only. If urine pregnancy results cannot be confirmed as negative, a serum pregnancy test will be required. ‡ If considered standard of care in your region.			

Product: MK-3475

Protocol/Amendment No.: Amendment 5, 21 October 2019

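### Two of the six MK-3475 doses (Weeks 4 and 16) have no scheduled chemistry panel, although the dose-hold rules depend on liver and kidney values

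*Combined protocol and SAP*

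**What the plan says.** The flow chart (7.1) places MK-3475 at Weeks 1, 4, 7, 10, 13 and 16. Its CMP row is marked at screening, Weeks 1, 7, 10, 13 and 19, discontinuation and the safety follow-up visit, and is blank at Weeks 4 and 16. Section 8.1.6.2.1 gives the same on-treatment schedule in words: "Biochemistry panel examining electrolytes, and liver enzymes will be performed on Day 1, Cycle 1 of MK-3475, at Weeks 7, 10 and 13", and again at the end of therapy in Week 19. CBC, by contrast, is scheduled on Day 1 of every cycle.

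Two rules make dosing depend on laboratory results. Section 8.1.3.1, which covers hematology, chemistry and urinalysis, requires results to be reviewed and "found to be acceptable prior to each dose of trial treatment". It also allows some lead time: "After Cycle 1, pre-dose laboratory procedures can be conducted up to 72 hours prior to dosing". Section 8.1.6.2.1 adds: "Treatment will not proceed unless laboratory values are acceptable".

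Table 3 (5.2.3.3) has a row for "AST, ALT, or Increased Bilirubin" and another for renal failure or nephritis. Each requires a hold at Grade 2 and, apart from a footnoted liver-metastasis exception, permanent discontinuation at Grade 3-4. The values needed (AST, ALT, bilirubin, creatinine, blood urea nitrogen) are in the chemistry column of Table 7.

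**The concern.** The rules assume a current liver and kidney result at every MK-3475 dose, but the schedule supplies one at only four of the six. At the other two, a site working from the flow chart has a CBC and a clinical assessment and nothing with which to grade a silent rise in transaminases or creatinine.

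Safety is the primary objective, and the primary summary in section 10.1 is the proportion of patients with each adverse event, by grade. Three things are at stake.

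- **Week 4.** Dose 2 is given with no chemistry since Day 1, or since a screening panel up to 10 days older. A persistent abnormality is first seen at Week 7. A transient one may never be recorded.
- **Week 16.** An abnormality that begins after the Week 13 panel is first seen at Week 19, when no dose remains to withhold.
- **The escalation count.** The 100 mg rule is worded in terms of held or stopped doses: "If two out of three or two out of six subjects develop toxicity that requires the dose to be withheld or discontinued". An abnormality found only after the last dose may not enter that count.

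**Working it through.** **Inputs.** Dosing weeks and CMP weeks come from 7.1, cross-checked against the text of 8.1.6.2.1. Visit windows come from 7.1 (Week 7 ±1 day; Weeks 4, 13, 16 and 19 ±3 days). The 10-day screening allowance is in 7.1 (footnote r) and 8.1.3.1. The number of subjects is 15.

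**Schedule side by side**

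| Week | 1 | 4 | 7 | 10 | 13 | 16 | 19 |
|---|---|---|---|---|---|---|---|
| MK-3475 | X | X | X | X | X | X | |
| CBC | X | X | X | X | X | X | X |
| Chemistry | X | – | X | X | X | – | X |

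**Count.** Dosing weeks {1, 4, 7, 10, 13, 16} minus chemistry weeks {1, 7, 10, 13, 19} = {4, 16}. That is 2 of 6 doses per subject. Across the trial the maximum is 15 × 2 = 30 of 15 × 6 = 90. The same count for CBC is 0 of 6. Because text and chart agree, the blanks are not a fault of table extraction.

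**Nominal gaps between panels.** Weeks 1 to 7: 6 × 7 = 42 days. Weeks 7 to 10 and 10 to 13: 3 × 7 = 21 days each. Weeks 13 to 19: 42 days.

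**Gaps with visit windows** (Day 1 as anchor, panels drawn on the visit day)

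- Weeks 1 to 7: 42 ± 1 = 41 to 43 days. If a screening panel 10 days old stands in for Day 1, the maximum is 43 + 10 = 53 days. Section 5.2.5 allows ±3 days for every MK-3475 dose. On that window the range is 42 ± 3 = 39 to 45 days, or at most 55 with the screening panel.
- Weeks 13 to 19: 42 ± (3 + 3) = 36 to 48 days. Drawing the Week 13 panel 72 hours before the dose can add 3 days, for a maximum of 51. The 72-hour allowance cannot lengthen the Week 1 to 7 gap: it applies only after Cycle 1, and an early Week 7 draw shortens that gap.

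**After adding panels at Weeks 4 and 16** (same convention)

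- Weeks 1 to 4: 21 ± 3, at most 24 days (24 + 10 = 34 with a screening panel).
- Weeks 4 to 7: 21 ± (3 + 1), at most 25 days.
- Weeks 13 to 16 and 16 to 19: 21 ± (3 + 3), at most 27 days.

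The longest gap after Day 1 falls from 42 to 21 days nominally, and from 48 to 27 days at the extremes of the flow-chart windows. Doses with a scheduled panel rise from 4 of 6 to 6 of 6.

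**The case against.** The strongest reply is that there is no contradiction. Section 8.1.3.1 does not say that every Table 7 panel is repeated before every dose. Section 8.1.6 sends the reader to the flow chart for visit requirements, and both chart and text deliberately separate CBC (every cycle) from chemistry (named weeks). On that reading, only the results that were scheduled must be acceptable. The reading is tenable, but it leaves the Table 3 liver and kidney holds with no current value at two doses. On the other reading, chemistry is already required and the schedule is wrong. Either way the protocol needs a change.

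Several points limit the consequence, and they stand:

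- Toxicity is assessed before each dose and unscheduled tests are allowed (8.1), so symptomatic or known abnormalities can still lead to a hold. Discretionary testing needs a prompt, however, and a silent abnormality gives none.
- The doses given with BCG (Weeks 7 and 10) and the first after it (Week 13) all have a panel. The gaps lie in the single-agent lead-in and tail, and 4.2.2 reports no dose-limiting toxicity in the cited single-agent phase 1 trial. Against this, 5.2.3.3 warns that events may come soon after the first dose or months after the last.
- A Week 16 panel could change at most one infusion, and two panels follow that dose (Week 19 and safety follow-up).
- The effect on escalation is modest. The Data Safety Review Team decides on escalation (5.2.3.1), sees all adverse event data once the first three subjects complete therapy (6.1), and applies Grade 4 rules that need no held dose (5.8). The two-subject rule could also be read as counting toxicity severe enough to warrant a hold, whether or not a dose remained.
- Appendix F of this amendment speaks of samples already collected and describes 200 mg dosing. Much of the treatment may therefore be past, and a change now would reach fewer than 15 subjects.

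**Conclusion.** The point holds. Chemistry is not scheduled at 2 of 6 MK-3475 doses, although the hold rules depend on it, and the nominal interval between panels doubles from 21 to 42 days at both ends of treatment. The count rests on the flow chart and the text, which agree. The figure of 30 of 90 doses assumes that all 15 subjects receive all six doses and that sites draw no more than the schedule asks.

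This is a gap in safety monitoring that should be closed. It does not undermine the trial. The size given is exposure to unmonitored doses; the documents offer no basis for estimating how many abnormalities would be missed. The main loss is a delayed hold or an unrecorded transient event. The effect on the escalation decision is secondary, because the review team sees the adverse event data anyway.

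**What to change.** Add a CMP at Week 4 and Week 16 to the flow chart and to 8.1.6.2.1, drawn within the existing 72-hour pre-dose window and reviewed before the infusion. State in 8.1.3.1 that this review includes chemistry, so that rule and schedule agree.

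Blood is already taken at both visits for CBC and correlative studies, so no extra visit or needle stick is needed. The cost is at most 15 × 2 = 30 additional panels, plus a protocol amendment with IRB approval (12.4.2).

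The change helps only subjects still to be dosed, and the documents do not say how many remain. If none do, the report should state how many doses were given without a pre-dose chemistry result, so that readers can judge the completeness of the liver and kidney adverse event data.

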8.1.6.2.3 Phone Monitoring

To monitor for systemic BCG infection, subjects will be called daily on days 2-4 of each BCG treatment cycle (Weeks 7-12). Subjects will be queried on symptoms which may indicate systemic infection. If clinically indicated, subject will be seen and clinically worked up for systemic infection and treatment started as indicated.

8.1.6.3 Unplanned Visits

Unplanned visit information will be collected as well. Information collected will include: disease symptoms and assessment/status, laboratory/imaging assessments, and toxicity assessments.

8.1.6.4 Post-Treatment Visits

An evaluation under anesthesia with cystoscopy, cytology, and random bladder biopsies (if indicated for positive findings on cystoscopy or cytology) will be performed at Week 19 (approximately 6 weeks after the last dose of BCG) to assess for response. Physical examination, performance status, as well as vital signs, will also be assessed at the Week 19 visit. Laboratory assessments will include hematology and chemistry as outlined in Section 7 – Trial Flow Chart and Table 7. Coagulation assessment (PT/PTT/INR) will be re-assessed, if resection/biopsy is indicated. Specimens needed for correlative studies will again be collected, including blood, urine, saliva and tumor (if biopsy is performed). The collection, storage, and processing of laboratory samples are detailed in the Procedure Manual.

The AUA IPSS and QOL questionnaires are also to be administered at Week 19 visit prior to any study procedures.

8.1.6.5 Treatment Discontinuation/Safety Follow-Up Visit

The Treatment Discontinuation Visit and Safety Follow-Up Visit include identical procedures and assessments. Subjects withdrawn from treatment prior to completion of the Treatment Period should undergo a Discontinuation Visit for safety purposes and may occur any time within 30 days of the subject discontinuing treatment, but preferably prior to the subject initiating a new treatment. The mandatory Safety Follow-Up Visit should be conducted approximately 30 days after the last dose of trial treatment or before the initiation of a new anti-cancer treatment, whichever comes first. All AEs that occur prior to the Safety Follow-Up Visit should be recorded. Subjects with an AE of Grade >1 will be followed until the resolution of the AE to Grade 0-1 or until the beginning of a new anti-neoplastic therapy,

Product: MK-3475

Protocol/Amendment No.: Amendment 5, 21 October 2019

whichever occurs first. SAEs that occur within 30 days of the end of treatment or before initiation of a new anti-cancer treatment should also be followed and recorded.

Assessments at the Discontinuation/Safety Follow-Up Visit include a full physical examination, ECOG Performance Status and vital signs. Laboratory assessments include hematology, chemistry, and urinalysis, as well as evaluation of thyroid function. Concomitant medications and toxicity assessment will be recorded as well.

